1. OBJECTIVES

1.1 Primary Objectives

1.1.1 To characterize the effects of hydroxychloroquine (HCQ) on plasma PAR-4 levels in adults with resectable solid tumors at the time of and after resection and to compare them to pre-HCQ treatment plasma levels

1.2 Secondary Objectives

1.2.1 To evaluate the toxicity profile and pharmacokinetics of hydroxychloroquine given in this setting

1.2.2 To assess the ability of hydroxychloroquine to alter PAR-4 expression in tumors.

2. BACKGROUND

2.1 Introduction: PAR-4

Prostate apoptosis response-4 (PAR-4, also called PAWR) is a tumor suppressor protein that induces apoptosis in diverse cancer cells but not in normal cells.¹ PAR-4 is ubiquitously expressed in normal cells and tissues, but is often inactivated, down-regulated or mutated in several types of cancers.² PAR-4 is located in various cell compartments, including the cytoplasm, endoplasmic reticulum (ER), and the nucleus, and both intracellular PAR-4 as well as secreted PAR-4 have been shown to play a role in apoptosis induction by caspase-dependent mechanisms.³ Moreover, PAR-4 sensitizes cells to the action of diverse therapeutic agents.⁴ Accordingly, loss of PAR-4 in tumors contributes to recurrent tumors and a decrease in overall patient survival.⁵ PAR-4 protein is secreted in cell culture-conditioned medium (CM) or systemically in mice by normal cells, and extracellular Par-4 binds to its receptor GRP78 on the cancer cell surface and induces apoptosis.^{2,6} By contrast, normal cells express low to undetectable levels of cell surface GRP78 and are resistant to apoptosis by extracellular PAR-4.^{2,6} Our recent studies have indicated that GRP78 levels can be increased on the surface of diverse cancer cells to overcome PAR-4-resistance by inhibition of NF- κ B activity, which is usually elevated in most cancer cells.⁶ Recombinant PAR-4 (made in *E. coli*) induces apoptosis of tumor cells and inhibits tumor growth in mice.⁷

2.2 Hydroxychloroquine

Chloroquine [CQ; (*RS*)-*N'*-(7-chloroquinolin-4-yl)-*N,N*-diethyl-pentane-1,4-diamine] is an antimalarial drug introduced into clinical practice in 1947 for the prophylactic treatment of malaria.⁸ CQ has been repurposed to treat inflammatory diseases such as rheumatoid arthritis and lupus. Hydroxychloroquine (HCQ) differs from chloroquine by the presence of a hydroxyl group at the N-ethyl substituent is beta-hydroxylated, but has similar pharmacokinetics to CQ, with quick gastrointestinal absorption and is eliminated by the kidney with minimal side effects on short term treatments. Side effects of chronic treatment are restricted to the eye. Overdose symptoms, which can occur within a half-hour of taking the medication, include convulsions, drowsiness, headache, heart problems or heart failure, difficulty breathing and vision problems. Both CQ and HCQ are potent inhibitors of autophagy, a cellular survival process during starvation to maintain cellular energy by degradation of unnecessary or dysfunctional

components through the actions of lysosomes. CQ and HCQ are lysosomotropic agents, which inhibit autophagy by raising the lysosomal pH and leads to inhibition of both fusion of autophagosome with lysosome and lysosomal protein degradation. Moreover, by inhibiting autophagy, CQ activates caspases and sensitizes the cells to apoptosis. These apoptosis sensitizing features of HCQ or CQ enhance the anti-tumor effects of a broad range of cancer therapeutics.^{9,10} In fact, CQ prophylaxis against malaria in Tanzania was associated with a reduction in the number of cases of Burkitt's lymphoma.¹¹ Accordingly, HCQ and CQ are being studied in a number of clinical trials that use these compounds either pre-operatively or in conjunction with chemotherapeutic agents or radiation (<http://www.cancer.gov/clinicaltrials/search/results?protocolsearchid=12327270>)

2.3 Rationale for Studying PAR-4 Expression in subjects treated with Chloroquine

As the baseline levels of PAR-4 secreted by normal cells are generally inadequate to cause massive apoptosis in cancer cells, drugs that bolster the secretion of PAR-4 would constitute an important therapeutic advance. Our recent studies identified several small molecules that show robust secretion of Par-4 in cell culture and mouse models, and secreted PAR-4 induces apoptosis of cancer cells.¹² However, these small molecules are not FDA-approved for human use. We therefore sought to identify FDA-approved small molecule drugs that show robust secretion of PAR-4 in normal cells and therefore can be repurposed for treatment of cancer. These studies (unpublished) identified HCQ as a potent inducer of PAR-4 secretion from normal cells under conditions that show no normal cell death. As normal cells in any patient far outnumber cancer cells, FDA-approved PAR-4 secretagogues may play a valuable role in elevating systemic and local levels of PAR-4 protein and thereby induce paracrine apoptosis in primary and metastatic tumors. Systemic PAR-4 is also expected to induce apoptosis in circulating cancer cells that contribute to metastasis. Because PAR-4 produces apoptosis in diverse tumors, and HCQ is expected to produce elevated levels of PAR-4 secretion in a broad range of patients to prevent the growth of tumors. Thus, our findings will potentially have broad clinical significance.

2.4 Correlative Studies Background

Studies in cell culture and mice indicated that HCQ induced robust secretion of PAR-4 in normal fibroblast and epithelial cell cultures, and elevated PAR-4 protein levels in the plasma of immunocompetent mice. Moreover, examination of plasma samples from renal cell carcinoma patients who were given HCQ (400 mg daily for 2 weeks) prior to surgery indicated that HCQ increased the secretion of PAR-4 protein levels in 4 of 5 patients (Figure 1). However, HCQ pharmacokinetics is highly variable and we expect an exposure dependent (area under the curve) effect on Par-4 secretion rather than a dose-dependent effect.

[figure not shown]

Figure 1. Chloroquine induces Par-4 secretion. A and B. Various cell lines such as mouse embryonic fibroblasts (MEFs, early passage 4 or 5), human primary prostate fibroblast cells (PrSC), human primary prostate epithelial cells (PrEC), human lung embryonic fibroblasts (HEL), human bronchial epithelial cells (HBEC) (A) or prostate cancer cell lines (B), were treated with the indicated amounts of chloroquine diphosphate (CQ) or vehicle (V) control for 24 h. The conditioned medium (CM), as well as the whole-cell lysates were subjected to Western blot analysis with the indicated antibodies. Collagen (Col1A1) was used as a loading control for protein secretion, as it is generally unchanged in response to the treatments. The samples were also subjected to SDS-PAGE and Coomassie blue staining to determine albumin levels in serum from the CM as another loading control. C. C57/BL6 mice were injected intraperitoneally with a single dose (50 mg/kg body weight) of CQ and serum samples were collected after 24 h and processed by Western blot analysis.

D. Plasma samples were collected from renal cell carcinoma patients who were treated with HCQ pre-operatively for 2-weeks at 400 mg/day were collected pre- and post-HCQ treatment at the University of Pittsburgh as part of a clinical trial on HCQ in 2010-2011. The archival (frozen) samples were processed by Western blot analysis at the University of Kentucky in 2013-2014.

2.5 Hypothesis

That hydroxychloroquine will induce at least 2-fold increase in systemic (plasma) PAR-4 levels compared to pre-treatment plasma levels in patients with resectable solid tumors.

3. PATIENT SELECTION

3.1 Eligibility Criteria

- 3.1.1 Patients must have a histologically confirmed or highly suspected (as determined by treating physician) solid tumor that is planned for surgical resection.
- 3.1.2 Age ≥ 18 years.
- 3.1.3 ECOG performance status ≤ 2 (Karnofsky $\geq 60\%$, see Appendix A).
- 3.1.4 Patients must be able to ingest oral medications (crushing and administering via PEG tube is acceptable).
- 3.1.5 Patients must have normal organ and marrow function as defined below:
- absolute neutrophil count $\geq 1,500/\text{mcL}$
 - platelets $\geq 100,000/\text{mcL}$
 - total bilirubin Less than 1.5 x ULN
 - AST(SGOT)/ALT(SGPT) $\leq 2.5 \times$ institutional upper limit of normal
 - creatinine less than institutional ULN
- OR
- Creatinine clearance $\geq 60 \text{ mL/min/1.73 m}^2$ for patients with creatinine levels above institutional normal.
- 3.1.6 Patients must be able to undergo surgical resection of their tumor as determined by the treating surgeon.
- 3.1.7 The effects of hydroxychloroquine on the developing human fetus are unknown. For this reason and because anti-malarial agents as well as other therapeutic agents used in this trial are known to be teratogenic, women of child-bearing potential and men must agree to use adequate contraception (hormonal or barrier method of birth control; abstinence) prior to study entry and for the duration of study participation. Should a woman become pregnant or suspect she is pregnant while she or her partner is participating in this study, she should inform her treating physician immediately. Men treated or enrolled on this protocol must also agree to use adequate contraception prior to the study, for the duration of study participation, and 4 months after completion of hydroxychloroquine administration.
- 3.1.8 Ability to understand and the willingness to sign a written informed consent document.

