3.2.10 Patients that are on enzyme-inducing anti-epileptic medications

3.3 Inclusion of Women and Minorities

Both men and women of all races and ethnic groups are eligible for this trial.

| Accrual Targets | | | | |
|---|------------|---|-------|-------|
| Ethnic Category | Sex/Gender | | | |
| | Females | | Males | Total |
| Hispanic or Latino | 1 | + | 1 | = 2 |
| Not Hispanic or Latino | 8 | | 8 | = 16 |
| Ethnic Category: Total of all subjects | 9 | + | 9 | = 18 |
| Racial Category | | | | |
| American Indian or Alaskan Native | 0 | + | 0 | = 0 |
| Asian | 1 | + | 1 | = 2 |
| Black or African American | 1 | + | 1 | = 2 |
| Native Hawaiian or other Pacific Islander | | + | | = |
| White | 7 | + | 7 | = 14 |
| Racial Category: Total of all subjects | 9 | + | 9 | = 18 |

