5.7 Duration of Follow Up

Patients will be followed for 30 days after surgery or 30 days after completion of the last dose of hydroxychloroquine if no surgery is completed. Patients removed from study for unacceptable adverse event(s) will be followed until resolution or stabilization of the adverse event. Follow-up visit should be combined with subject standard of care post-operative visit. If that visit occurs prior to the 30 days post op, subject should be contacted 30 days or after completion of the last dose for adverse event assessment.

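### Section 3.1.7 gives men 4 months of contraception after hydroxychloroquine but women only about 30–31 days on the same rationale; pregnancy notification stops early too, and the only pregnancy test may be 28 days old at first dose

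*Combined protocol and SAP*

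**What the plan says.** Section 3.1.7 opens with the reason: "The effects of hydroxychloroquine on the developing human fetus are unknown", together with a statement that drugs of this class are teratogenic. On that basis "women of child-bearing potential and men must agree to use adequate contraception" "prior to study entry and for the duration of study participation". A later sentence repeats the duty for men and lengthens it: "for the duration of study participation, and 4 months after completion of hydroxychloroquine administration". No matching extension is given for women.

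The same section tells a woman to inform her physician at once if she becomes, or thinks she may be, pregnant "while she or her partner is participating in this study". That wording covers female patients and partners of male patients, but only during participation.

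The nearest statement of when participation ends is section 5.7: "Patients will be followed for 30 days after surgery or 30 days after completion of the last dose of hydroxychloroquine", the second limb applying when no surgery takes place. There is one exception: "Patients removed from study for unacceptable adverse event(s) will be followed until resolution or stabilization of the adverse event". Under section 5.2 dosing lasts 14 days, may be extended by 7, and ideally stops the day before surgery.

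Section 3.2.8 excludes pregnant women. The Study Calendar has one pregnancy test, in the Pre-Study column. Section 5.1 allows laboratory tests up to 4 weeks before treatment starts, while the calendar text puts baseline evaluations 2 to 4 weeks before.

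**The concern.** Three rules that serve one purpose do not fit together.

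First, women who take the drug have a shorter post-dose contraception period than men who take it, on an identical stated rationale. Nothing in the available text separates the sexes. The only fetal-exposure data cited, the animal findings in section 3.2.8, concern transfer across the placenta, which is the maternal route.

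Second, the duty to report a pregnancy stops before the men's duty to prevent one. A partner's pregnancy in roughly months 2 to 4 would occur while the protocol still requires contraception, but the notification sentence would not ask for it to be reported. This holds whichever contraception length is right.

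Third, no scheduled test stands between the Pre-Study test and the first dose. A pregnancy too early to be detected at screening, or one that began afterwards, could be exposed to the whole course.

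What is at stake is a safety commitment that participants accept at entry, and the sponsor's knowledge of any exposed pregnancy. Error rates and the primary analysis are not involved.

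**Working it through.** **Inputs**

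- Men's post-dose period: 4 months (3.1.7). This is the only post-treatment contraception figure in the documents, and no derivation is given, so there is nothing to reproduce.
- End of follow-up: 30 days after surgery, or 30 days after the last dose if there is no surgery (5.7).
- Interval from last dose to surgery, *g*: 1 day on the preferred schedule (5.2). With no surgery, take *g* = 0. Values of 7 and 14 days are assumed, to show sensitivity.
- Age of baseline laboratory tests at first dose: at most 4 weeks (5.1); 2 to 4 weeks in the calendar text.
- Accrual target: "Ethnic Category: Total of all subjects | 9 | + | 9 | = 18", that is 9 women and 9 men (3.3).

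Reading the end of participation as the end of 5.7 follow-up is an assumption.

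**Step 1: men.** 4 × 365.25/12 = 121.75 days. Counted by calendar month, the period is 120 days (1 February to 1 June, non-leap year) to 123 days (1 July to 1 November).

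**Step 2: women.** Days of cover after the last dose = 30 + *g*. The difference from men is 121.75 − (30 + *g*).

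| Case | Women's cover (days) | Difference from men (days) | Range by calendar month |
|---|---|---|---|
| Surgery the day after last dose | 30 + 1 = 31 | 121.75 − 31 = 90.75 | 89 to 92 |
| No surgery | 30 + 0 = 30 | 121.75 − 30 = 91.75 | 90 to 93 |
| Surgery 7 days after last dose (assumed) | 30 + 7 = 37 | 121.75 − 37 = 84.75 | 83 to 86 |
| Surgery 14 days after last dose (assumed) | 30 + 14 = 44 | 121.75 − 44 = 77.75 | 76 to 79 |

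**Step 3: notification.** For a male patient, notification ends on the day that 30 + *g* gives, while his contraception runs to day 121.75. The share of his post-dose period left outside is 90.75/121.75 = 74.5% with surgery the next day, and 91.75/121.75 = 75.4% with no surgery.

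**Step 4: age of the pregnancy test.** The maximum at first dose is 4 × 7 = 28 days, under both 5.1 and the calendar. Section 5.1 sets no minimum, so the range there is 0 to 28 days. By the day-14 dose a test at the maximum is 28 + 13 = 41 days old, and by a day-21 dose 28 + 20 = 48. A 7-day window would cut the maximum at first dose by 28 − 7 = 21 days.

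**The case against.** The strongest reply is that no harm is shown. The documents give no half-life or washout time for the drug, so nothing in them says that 30 days is too short for women. The difference could equally mean that the men's period is longer than it needs to be. That stands, and it limits the point to an unexplained difference. A reader might infer from the five-month retention described in section 3.2.8 that women need at least that long. The documents do not support this: the retention was in fetal ocular tissue of animals after placental transfer, and it does not give a maternal washout period.

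Second, section 4.3 treats the consent form as part of the protocol, and those pages are not in the review copy. They may set a longer period for women, or later reporting. That is a fair caution, but such wording would not make 3.1.7 or the calendar consistent.

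Third, a reader might say that the women's period has no end at all, because the term is not defined. That goes too far, since 5.7 supplies a workable end. It is less firm for a patient removed for an adverse event, whose follow-up is open-ended, or for one who withdraws under 5.6 and 5.8.

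Fourth, a 30-day horizon matches the windows for dose-limiting toxicity (5.4) and serious adverse events (7.5.1), and nothing bars a later report. This makes the notification rule understandable. It does not explain asking men to avoid conception for three months beyond it.

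Fifth, the calendar's 2-to-4-week wording might be read as making the test at least 14 days old. Section 5.1 has no such floor, so only the 28-day maximum is secure. Contraception before entry and the duty to report a suspected pregnancy reduce the risk of dosing an undetected pregnancy, but do not remove it.

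**Conclusion.** The point holds as a minor one. On one stated rationale, women's contraception ends about 30–31 days after the last dose and men's at about 122, a difference of about 91 days with surgery the next day and 92 with none. No reason is given in the available text. Notification stops the same 91 to 92 days before the men's period ends, about 75% of it. The only scheduled pregnancy test may be 28 days old at first dose.

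These figures assume that participation ends with 5.7 follow-up and, for the 91-day figure, that dosing stops the day before surgery. A longer interval to surgery narrows the difference, to about 78 days at an assumed 14 days.

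A reader might infer that women in this trial are shown to be under-protected, or that 4 months is the required length. The documents support neither. The number of women of child-bearing potential is not given; the accrual target is 9 women in all.

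**What to change.** 1. In 3.1.7, count women's contraception from the last hydroxychloroquine dose, by default for the same 4 months as men. If there is a clinical reason for another length, document it and state that length explicitly.
2. Run the pregnancy-notification sentence to the end of the contraception period, for patients and for partners of male patients.
3. By a calendar footnote, require the existing pregnancy test shortly before first dispensing, and override the 2-to-4-week wording for that test. Within 7 days is my suggestion; the documents set no figure.
4. Match the consent wording.

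The editing cost is two sentences, one footnote and the consent text. The burden is about 3 more months of contraception for at most 9 women on the accrual target, a longer notification period, and tighter timing of one test. The test should not be assumed to share the Pre-Study correlative blood draw, which may fall outside a 7-day window. It may have to be done when the drug is dispensed, and where dispensing would not otherwise bring the patient in, that could mean an extra visit. The PAR-4 endpoint, the dose-finding rule and n = 18 do not change.

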3.2 Exclusion Criteria

- 3.2.1 Patients with metastatic cancer and/or cancer that is not amenable to surgery (i.e. must be curative intent; locally advanced is acceptable).
- 3.2.2 Patients with significant malabsorption as determined by the treating physician.
- 3.2.3 Patients who are receiving any other investigational agents.
- 3.2.4 Patients with known brain metastases are excluded from this clinical trial because of their poor prognosis and because they often develop progressive neurologic dysfunction that would confound the evaluation of neurologic and other adverse events. Patients with primary brain tumors amenable to surgery are allowed on this protocol.
- 3.2.5 History of allergic reactions attributed to compounds of similar chemical or biologic composition to hydroxychloroquine.
- 3.2.6 Caution should be taken with the use of hydroxychloroquine and any drugs known to interact with it (Appendix C). Because the lists of these agents are constantly changing, it is important to regularly consult a frequently-updated list such as <http://medicine.iupui.edu/clinpharm/ddis/table.aspx>; medical reference texts such as the Physicians' Desk Reference may also provide this information. As part of the enrollment/informed consent procedures, the patient will be counseled on the risk of interactions with other agents, and what to do if new medications need to be prescribed or if the patient is considering a new over-the-counter medicine or herbal product. Appendix C contains a list of known drug interactions with hydroxychloroquine.
- 3.2.7 Uncontrolled intercurrent illness including, but not limited to, ongoing or active infection, symptomatic congestive heart failure, unstable angina pectoris, cardiac arrhythmia, or psychiatric illness/social situations that would limit compliance with study requirements.
- 3.2.8 Pregnant women are excluded from this study. While hydroxychloroquine has not been formally assigned to a pregnancy category by the FDA, animal studies have revealed that the drug passed rapidly across the placenta, accumulated selectively in the melanin structures of the fetal eyes, and was retained in the ocular tissues for five months after the drug had been eliminated from the rest of the body. There are no controlled data in human pregnancy. Because there is an unknown but potential risk for adverse events in nursing infants secondary to treatment of the mother with hydroxychloroquine, breastfeeding should be discontinued if the mother is treated with hydroxychloroquine. These potential risks may also apply to other agents used in this study.
- 3.2.9 HIV-positive patients on combination antiretroviral therapy are ineligible because of the potential for pharmacokinetic interactions with hydroxychloroquine. In addition, these patients are at increased risk of lethal infections when treated with marrow-suppressive therapy. Appropriate studies will be undertaken in patients receiving combination antiretroviral therapy when indicated.

3.2.10 Patients that are on enzyme-inducing anti-epileptic medications

3.3 Inclusion of Women and Minorities

Both men and women of all races and ethnic groups are eligible for this trial.

| Accrual Targets | | | | |
|---|------------|---|-------|-------|
| Ethnic Category | Sex/Gender | | | |
| | Females | | Males | Total |
| Hispanic or Latino | 1 | + | 1 | = 2 |
| Not Hispanic or Latino | 8 | | 8 | = 16 |
| Ethnic Category: Total of all subjects | 9 | + | 9 | = 18 |
| Racial Category | | | | |
| American Indian or Alaskan Native | 0 | + | 0 | = 0 |
| Asian | 1 | + | 1 | = 2 |
| Black or African American | 1 | + | 1 | = 2 |
| Native Hawaiian or other Pacific Islander | | + | | = |
| White | 7 | + | 7 | = 14 |
| Racial Category: Total of all subjects | 9 | + | 9 | = 18 |

4. REGISTRATION PROCEDURES

4.1 Protocol Review and Monitoring Committee and Institutional Review Board Review

Before implementing this study, the protocol, the proposed informed consent form and other information to subjects, must be reviewed by the Markey Cancer Center's Protocol Review and Monitoring Committee and the University of Kentucky Institutional Review Board (IRB). A signed and dated statement that the protocol and informed consent have been approved by the IRB must be maintained in the Markey Cancer Center Clinical Research and Data Management Shared Resource Facility (MCC CRDM SRF) regulatory binder. Any amendments to the protocol, other than administrative ones, must be reviewed and approved by the PRMC, study sponsor and the UK IRB.

